**Table 2. Schedule of Assessments for Part B, Double-Blind, Placebo-Controlled Part of the Study**

Assessment	Screening	Treatment Phase												Post-Treatment Phase		
	Screening Visit	Dosing Visit 1			Dosing Visit 2		Dosing Visit 3		Dosing Visit 4		Dosing Visit 5		Follow-Up			
		Dose 1		Dose 2	Dose 3	Dose 4	Dose 5	Dose 6		Dose 7	Dose 8	Dose 9	Dose 10	Visit Day 7	TFU	
Time Relative to Dose	-24 to first dose	- 2h to 0	0 h	+4-5h Or +6-8h					0 h	+4-5 h or +6-8h				Last Dose	+40-48h Post-Dose 10	Day 12
Written Informed Consent a	X															
RSV Rapid Diagnostic Test	X															
Inclusion / Exclusion Criteria	X	X														
Demographics b	X															
Medical History	X															
Prior Medication Review	X															
Physical Examination c	X	X													X	
Hydration Status d	X	X				X		X			X*		X*		X	
Body Weight / Length / Head Circumference	X														X	
Vital Signs e	X	X	X	X	X	X	X	X	X	X	X*	X*	X*	X*	X	

This document is confidential.

Assessment	Screening	Treatment Phase												Post-Treatment Phase		
	Screening Visit	Dosing Visit 1			Dosing Visit 2		Dosing Visit 3			Dosing Visit 4		Dosing Visit 5		Follow-Up		
		Dose 1	Dose 2	Dose 3	Dose 4	Dose 5	Dose 6	Dose 7	Dose 8	Dose 9	Dose 10	Visit Day 7	TFU			
Time Relative to Dose	-24 to first dose	- 2h to 0	0 h	+4-5h Or +6-8h					0 h	+4-5 h or +6-8h				Last Dose	+40-48h Post-Dose 10	Day 12
12-Lead ECG f	X			X		X		X		X		X*		X*	X	
RSV Clinical Scoring System g	X	X				X		X				X*		X*	X	
Record RSV Signs and Symptoms h	X	X			X	X	X	X	X			X*	X*	X*	X*	X
Record Supplemental O 2		X			X	X	X	X	X			X*	X*	X*	X*	
Pulse Oximetry on Room Air		X			X	X	X	X	X			X*	X*	X*	X*	X
Adapted ReSVinet Scale for Parental Use i	X														X	
Safety Laboratory Tests (Clinical Chemistry and Haematology) j	X														X	
Urinalysis	X														X	
Randomisation for Eligible Subjects		X														

This document is confidential.

Assessment	Screening	Treatment Phase												Post-Treatment Phase		
	Screening Visit	Dosing Visit 1			Dosing Visit 2		Dosing Visit 3			Dosing Visit 4		Dosing Visit 5		Follow-Up		
		Dose 1	Dose 2	Dose 3	Dose 4	Dose 5	Dose 6	Dose 7	Dose 8	Dose 9	Dose 10	Visit Day 7	TFU			
Time Relative to Dose	-24 to first dose	- 2h to 0	0 h	+4-5h Or +6-8h					0 h	+4-5 h or +6-8h				Last Dose	+40-48h Post-Dose 10	Day 12
PK Blood Sample k				X l	X m				X	X l	X m				X	
Nasopharyngeal Swab n		X			X	X	X	X	X		X o	X *	X *	X *	X	
Concomitant Medication Review	X	X	X	X	X	X	X	X	X	X	X	X	X	X	X	X
AEs Review	X	X	X	X	X	X	X	X	X	X	X	X	X	X	X	X
Study Medication Administration p			X		X	X	X	X	X		X	X	X	X		

Abbreviations: ECG = electrocardiogram; h = hours; PK = pharmacokinetic; RSV = respiratory syncytial virus; TFU = Telephone Follow-up Visit.

**Notes: All procedures and assessments are presented against the Dosing Visit at which they should be conducted. The actual day(s) on which the visit falls is dependent upon the time that investigational medicinal product (IMP) is administered during Dosing Visit 1. The Follow-up +40-48h Post-Dose 10 on Visit Day 7 could therefore occur on Study Day 7 or 8, depending on when the subject received his or her first Dose of IMP. Observations (SpO2, viral signs, inspection of RSV symptoms) should precede any procedures that manipulate the subject (physical examination, nasopharyngeal swabs, PK sampling). For the physical examination, listen to the lungs first. In any event, the order should be consistent for all the assessment days.**

a Written informed consent includes the consent for participating in Part B of the study and the written informed consent for the optional Sponsor-provided commercial RSV test.

b Demographic data to be collected: date of birth, gender, race and ethnicity.

This document is confidential.

- c Physical examination may also include a symptom-directed examination, general condition, lung auscultation, and respiratory muscles retractions (Protocol Section 10.1.3.8). For days when IMP is administered, physical examination should be conducted before a dose of IMP is administered.
- d Refer to Protocol Appendix 17.5 for the Dehydration Status Evaluation.
- e Vital signs include body temperature, systolic and diastolic blood pressure, respiratory rate, heart rate and should be conducted before PK and nasopharyngeal swab samples, for the respective time points, are taken. For the days without PK and nasopharyngeal swab samples, vital signs should be taken before a dose of IMP is administered.
- f 12-Lead ECG to be performed using the centrally provided ECG machine and before PK and nasopharyngeal swab samples are taken. For days when IMP is administered ECG should be performed before a dose of IMP is administered
- g Refer to Protocol Appendix 17.1 for the RSV Clinical Scoring System. Note: this assessment is to be done only when subject is hospitalised.
- h Refer to Protocol Appendix 17.4 for RSV signs and Symptoms
- i Refer to Protocol Appendix 17.2 for the Adapted version of ReSVinet scale for parental use.
- j At Screening, the AST/ALT values should be obtained from the local laboratory. A blood sample will still need to be sent to the Central laboratory.
- k The actual day for taking each PK sample is dependent on the time when IMP is administered on Visit 1 (Day 1) (morning versus afternoon versus evening); e.g., if the subject received their first dose of IMP at 22:00 on Day 1, the post-dose samples due to be taken at 4-5 h, 6-8 h, 12 h, and 18-24 h would be taken on Day 2 from 02:00 to 03:00, 04:00 to 06:00, 10:00, and 16:00 to 22:00, respectively (Table 5).
- l These PK samples will be defined after PK Analysis of Part A. One of those two samples will be requested, the other one will not be required (Table 5).
- m The 12 hour PK sampling window is 30 minutes (Table 5).
- n See Table 4 for nasopharyngeal swab sample schedule.
- o If the subject is discharged from hospital, a nasopharyngeal swab sample should be obtained prior to discharge if the parents/legal guardians are unlikely to return for the next visit. Note: this sample is not required if the previous sample was taken less than 12 hours before the subject is discharged (Table 4).
- p The times of the prior feeding and first feeding after dosing should be recorded. IMP should be administered every 12 hours or as dosing regimen recommended by the DSMC with a time window of  $\pm$  30 minutes.
- \* Procedure to be done if subject is in the hospital.

This document is confidential.

**Table 3. Schedule of Assessments for Part C**

Assessment	Screening	Treatment Phase												Post-Treatment Phase			
		Screening Visit	Dosing Visit 1			Dosing Visit 2		Dosing Visit 3		Dosing Visit 4		Dosing Visit 5		Follow-Up			
			Dose 1	Dose 2	Dose 3	Dose 4	Dose 5	Dose 6	Dose 7	Dose 8	Dose 9	Dose 10	Visit Day 7	Visit Day 14	Visit Day 28		
Time Relative to Dose	-24 to first dose	-2 to 0 h	0 h	+4-5 h Or +6-8 h					0 h	4-5 h Or +6-8 h				Last Dose	+40-48 h Post-Dose 10	Day 14	Day 28
Written Informed Consent a	X																
Inclusion / Exclusion Criteria	X	X															
RSV Rapid Diagnostic Test	X																
Demographics b	X																
Medical History	X																
Prior Medication Review	X																
Physical Examination c	X	X												X			
Hydration Status d	X	X			X		X			X*		X*		X			
Body Weight / Length / Head Circumference	X													X	X	X	
Vital Signs e	X	X		X	X	X	X	X	X	X	X*	X*	X*	X*	X	X	X

This document is confidential.

Assessment	Screening	Treatment Phase											Post-Treatment Phase					
		Screening Visit	Dosing Visit 1			Dosing Visit 2		Dosing Visit 3		Dosing Visit 4		Dosing Visit 5		Follow-Up				
			Dose 1		Dose 2	Dose 3	Dose 4	Dose 5	Dose 6		Dose 7	Dose 8	Dose 9	Dose 10	Visit Day 7	Visit Day 14	Visit Day 28	
Time Relative to Dose	-24 to first dose	-2 to 0 h	0 h	+4-5 h Or +6-8 h					0 h	4-5 h Or +6-8 h				Last Dose	+40-48 h Post-Dose 10	Day 14	Day 28	
12-Lead ECG f	X			X		X		X		X		X*		X*	X			
RSV Clinical Scoring System g	X	X				X		X				X*		X*	X	X	X	
Record RSV Signs and Symptoms h	X	X			X	X	X	X	X			X*	X*	X*	X*	X	X	X
Record Supplemental O 2		X			X	X	X	X	X			X*	X*	X*	X*			
Pulse Oximetry on Room Air		X			X	X	X	X	X			X*	X*	X*	X*			
Adapted ReSVinet Scale for Parental Use i	X														X			
Safety Laboratory Tests (Clinical Chemistry, and Haematology) j	X														X			
Urinalysis	X														X			
Randomisation for Eligible Subjects		X																

This document is confidential.

**Statistical Analysis Plan for Interventional Studies**

Sponsor: ReViral Ltd; Protocol No.: REVC003

Assessment	Screening	Treatment Phase											Post-Treatment Phase				
		Screening Visit	Dosing Visit 1			Dosing Visit 2		Dosing Visit 3		Dosing Visit 4		Dosing Visit 5		Follow-Up			
			Dose 1		Dose 2	Dose 3	Dose 4	Dose 5	Dose 6		Dose 7	Dose 8	Dose 9	Dose 10	Visit Day 7	Visit Day 14	Visit Day 28
Time Relative to Dose	-24 to first dose	-2 to 0 h	0 h	+4-5 h Or +6-8 h					0 h	4-5 h Or +6-8 h				Last Dose	+40-48 h Post-Dose 10	Day 14	Day 28
PK Blood Sample k								X	X l					X			
Nasopharyngeal Swab m		X			X	X	X	X	X		X n*	X *	X *	X *	X	X	X
Concomitant Medication Review	X	X	X	X	X	X	X	X	X	X	X *	X *	X *	X *	X	X	X
AEs Review	X	X	X	X	X	X	X	X	X	X	X	X	X	X	X	X	X
Study Medication Administration o			X		X	X	X	X	X		X	X	X	X			

Footnotes appear on next page.

This document is confidential.

Abbreviations: ECG = electrocardiogram; h = hours; PK = pharmacokinetic; RSV = respiratory syncytial virus.

**Notes: All procedures and assessments are presented against the Dosing Visit at which they should be conducted. The actual day(s) on which the visit falls is dependent upon the time that investigational medicinal product (IMP) is administered during Dosing Visit 1. The Follow-up +40-48h Post-Dose 10 on Visit Day 7 could therefore occur on Study Day 7 or 8, depending on when the subject received his or her first Dose of IMP.**

- a Written informed consent includes the consent for participating in Part C of the study and the written informed consent for the optional Sponsor-provided commercial RSV test.
- b Demographic data to be collected: date of birth, gender, race and ethnicity.
- c Physical examination may also include a symptom-directed examination, general condition, lung auscultation, and respiratory muscles retractions (Protocol Section 10.1.3.8). For days when IMP is administered, physical examination should be conducted before a dose of IMP is administered.
- d Refer to Protocol Appendix 17.5 for the Dehydration Status Evaluation.
- e Vital signs include body temperature, systolic and diastolic blood pressure, respiratory rate, heart rate and should be conducted before PK and nasopharyngeal swab samples, for the respective time points, are taken. For the days without PK and nasopharyngeal swab samples, vital signs should be taken before a dose of IMP is administered.
- f 12-Lead ECG to be performed using the centrally provided ECG machine and before PK and nasopharyngeal swab samples are taken. For days when IMP is administered ECG should be performed before a dose of IMP is administered
- g Refer to Protocol Appendix 17.1 for the RSV Clinical Scoring System. Note: this assessment is to be done only when subject is hospitalised.
- h Refer to Protocol Appendix 17.4 for RSV signs and Symptoms
- i Refer to Protocol Appendix 17.2 for the Adapted version of ReSVinet scale for parental use.
- j At Screening, the AST/ALT values should be obtained from the local laboratory. A blood sample will still need to be sent to the Central laboratory.
- k The actual day for taking each PK sample is dependent on the time when IMP is administered on Visit 1 (Day 1) (morning versus afternoon versus evening); e.g., if the subject received their first dose of IMP at 22:00 on Day 1, the post-dose samples due to be taken at 4-5 h, 6-8 h, 12 h, and 18-24 h would be taken on Day 2 from 02:00 to 03:00, 04:00 to 06:00, 10:00, and 16:00 to 22:00, respectively (Table 5).
- l These PK samples will be defined after PK Analysis of Part A. One of those two samples will be requested, the other one will not be required (Table 5).
- m See Table 4 for nasopharyngeal swab sample schedule.
- n If the subject is discharged from hospital, a nasopharyngeal swab sample should be obtained prior to discharge if the parents/legal guardians are unlikely to return for the next visit. Note: this sample is not required if the previous sample was taken less than 12 hours before the subject is discharged (Table 4).
- o The times of the prior feeding and first feeding after dosing should be recorded. IMP should be administered every 12 hours or as dosing regimen recommended by the DSMC with a time window of  $\pm$  30 minutes.
- \* Procedure to be done if subject is in the hospital.

This document is confidential.

**Table 4. Nasopharyngeal Sampling Schedule for the Study**

Part	Dosing Visit 1				Dosing Visit 2	Dosing Visit 3	Dosing Visit 4	Dosing Visit 5	Visit Day 7	Visit Day 14	Visit Day 28
	-2 h to 0 Pre-Dose	12 h Post Dose 1	1 sample collected 24 h post-dose	2 samples: 1 collected at 36 and 1 at 48 h Post Dose 1							
A	-2 h to 0 Pre-Dose	12 h Post Dose 1	1 sample collected 24 h post-dose	2 samples: 1 collected at 36 and 1 at 48 h Post Dose 1	NA	NA	NA	NA	NA	NA	NA
B	-2 h to 0 h Pre-Dose	12 h Post Dose 1 (pre-dose 2)	NA	NA	1 sample collected prior to each dose; 2 samples in total b	1 sample collected prior to each dose; 2 samples in total ab	1 sample collected prior to each dose; 2 samples in total ab	1 sample collected prior to each dose; 2 samples in total ab	+40-48 h post-Dose 10	NA	NA
C	-2h to 0 pre-dose b	12 h Post Dose 1 (pre-dose 2) b	NA	NA	1 sample collected prior to each dose; 2 samples in total b	1 sample collected prior to each dose; 2 samples in total ab	1 sample collected prior to each dose; 2 samples in total ab	1 sample collected prior to each dose; 2 samples in total ab	+40-48h post Dose 10	1 Sample	1 Sample

Abbreviations: h = hours; IMP = investigational medicinal product; NA = not applicable.

This document is confidential.

**Notes:**

- **All procedures and assessments are presented against the Dosing Visit at which they should be conducted. The actual day(s) on which the visit falls is dependent upon the time that investigational medicinal product (IMP) is administered during Dosing Visit 1. The Follow-up +40-48h Post-Dose 10 on Visit Day 7 could therefore occur on Study Day 7 or 8, depending on when the subject received his or her first Dose of IMP.**

- **CCI** [Redacted]

a If the subject is discharged from hospital, a nasopharyngeal swab sample should be obtained prior to discharge if the parents/legal guardians are unlikely to return for the next visit. Note: This sample is not required if the previous sample was taken less than 12 hours before the subject is discharged.

b Nasopharyngeal swab sampling window is 60 minutes.

\* Procedure to be done if subject is in the hospital

This document is confidential.

**Table 5. PK Sampling Schedule for the Study**

Part	Treatment Phase					Post Treatment Phase	Total Number of Samples
	Dosing Visit 1	Dosing Visit 2	Dosing Visit 3	Dosing Visit 4	Dosing Visit 5	Visit Day 7	
A: Single Dose	4-5h, 6-8h, 12h a , 18-24h, 48h	NA	NA	NA	NA	NA	5
B*: Multiple Dose	4-5h or 6-8 h Post-Dose 1, 12h a Post-Dose 1 (Pre-Dose 2)	NA	Pre-Dose 6, 4-5h or 6-8h Post-Dose 6.	12h a Post-Dose 6 (Pre-Dose 7)	NA	40-48h Post-Dose 10	6
C**: Multiple Dose		NA	Pre-Dose 6 4-5h or 6-8h Post-Dose 6	NA	NA	40-48h Post-Dose 10	3

Abbreviations: h = hours; IMP = investigational medicinal product; NA = not applicable; PK = pharmacokinetic.

Notes: **All procedures and assessments are presented against the Dosing Visit at which they should be conducted. The actual day(s) on which the visit falls is dependent upon the time that investigational medicinal product (IMP) is administered during Dosing Visit 1. The Follow-up +40-48h Post-Dose 10 on Visit Day 7 could therefore occur on Study Day 7 or 8, depending on when the subject received his or her first Dose of IMP.**

\*For PK Part B: After the review of PK analysis from Part A, it will be decided if the PK sample after the First Dose will be taken 4-5h Post Dose 1 or 6-8h Post-Dose 1. The same time point will be taken on Dosing Visit 3 (either 4-5h or 6-8h Post-Dose 6). Based on the Part A PK analysis, it will be decided if the Samples planned relative to Dose 6 should stay as planned or shifted relative to Dose 10 with the same time structure. In case the PK samples are shifted relative to Dose 10, then an additional PK sample 18-24h Post Dose 10 will be taken.

\*\* For PK Part C: The same PK time point Post-Dose 6 will be taken as in Part B, either 4-5h or 6-8h Post-Dose 6. Based on the Part A PK analysis, it will be decided if the samples planned relative to Dose 6 should stay as planned or shifted relative to Dose 10 with the same time structure. In case the PK samples are shifted relative to Dose 10 then an additional PK sample 18-24h Post Dose 10 will be taken.

a The 12-hour PK sampling window is 30 minutes.

This document is confidential.

## 4. Endpoints

### 4.1. Primary Endpoints

Safety and tolerability parameters to be assessed for study Parts A and B will include, but are not limited to:

- AEs, treatment emergent AEs (TEAEs), serious AEs (SAEs), and withdrawals due to TEAEs
- Physical examinations
- Vital sign parameters (i.e., systolic and diastolic blood pressure, temperature, respiratory rate, heart rate, and pulse oximetry), and changes from baseline in these parameters at predefined time points
- Laboratory tests (haematology, chemistry, and urinalysis test results) and changes from baseline in these parameters, at predefined time points
- ECG measurements and changes from baseline in these parameters at predefined time points

### 4.2. Secondary Endpoints

Secondary endpoints (primary endpoints in Spain) related to PK for study Parts A and B will include but are not limited to:

- Time to maximum plasma concentration ( $t_{max}$ )
- Maximum observed plasma concentration ( $C_{max}$ )
- Area under the plasma concentration time curve from time zero to 12 hours ( $AUC_{0-12}$ )
- Area under the plasma concentration time curve from time zero to last measurable plasma concentration ( $AUC_{0-t}$ )
- Terminal half-life ( $t_{1/2}$ )
- Area under the plasma concentration time curve from time zero to infinity ( $AUC_{0-\infty}$ )
- Predicted plasma clearance
- Apparent volume of distribution of the drug after extravascular administration (V/F)
- Trough concentration at the end of 1st dosing interval ( $C_{12}$ ) (data permitting)

In addition for Part B:

- Accumulation ratio, percentage fluctuation
- Area under the plasma concentration time curve from time zero to the end of last dosing interval ( $AUC_{0-\tau}$ )
- Average plasma concentration over dosing interval ( $C_{ave}$ )

This document is confidential.

- Minimum observed plasma concentration ( $C_{min}$ )
- Plasma trough concentration ( $C_{trough}$ )
- Any other relevant parameters

Secondary endpoints related to assessment of antiviral activity and efficacy for study Part B include but are not limited to:

- RSV viral load measured in nasopharyngeal swabs by reverse transcriptase quantitative polymerase chain reaction (RT-qPCR)
- RSV viral load measured in nasopharyngeal swabs by cell-based infectivity assay (CBIA)
- Time to resolution of symptoms
- Time to improvement evaluated by reduction in severity of symptoms
- Reduction in severity of symptoms by RV521, compared to placebo, measured by a composite score over time

#### 4.3. Exploratory Endpoints

CCI

- [REDACTED]
- [REDACTED]

#### 4.4. Endpoints for Part C

Endpoints for study Part C include but are not limited to:

##### Primary Endpoints for Part C

- Time to resolution of symptoms
- Time to improvement of symptoms
- Reduction in severity of symptoms by RV521, compared to placebo, measured by a composite score over time
- Use of supplemental oxygen, including, but not limited to, duration and maximum level of oxygen provided

##### Secondary Endpoints for Part C

- Safety of RV521 compared to placebo assessed by incidences of AEs, discontinuations due to AEs, SAEs, and clinically significant changes in laboratory tests
- Comparison between RV521 and placebo for changes in viral load over time as for Part B
- CCI [REDACTED]

This document is confidential.

- CCI [REDACTED]

This document is confidential.

## 5. Analysis Populations

### 5.1. Safety Population

The Safety Population will include all subjects who received at least 1 dose of IMP (RV521 or placebo). The Safety Population is the primary population for the analysis of safety data. Analysis will be according to actual treatment received.

### 5.2. mITT Population

The Modified Intent-to-Treat (mITT) Population in Part A will include all subjects enrolled in the study who have an RT-qPCR viral load measurement and/or CBIA, if available, for at least 1 time point including baseline pre-dose at Dosing Visit 1.

The mITT Population in Parts B and C will include all subjects who received at least 1 dose of IMP (RV521 or placebo) and have a pre-treatment positive RSV nasopharyngeal swab confirmed by the central laboratory and agreed by the project team during blind data review meeting. Potential inclusion of subjects who have not completed at least 6 doses of IMP will be decided by the project team during blind data review meeting.

Subjects will be analysed according to randomised treatment. The mITT Population is the primary population for the analysis of efficacy and PD data.

### 5.3. PK Population

The PK Population will include all subjects who receive IMP and have at least 1 post-dose PK concentration measurement. The PK Population is the primary population for the analysis of PK data. Analysis will be according to actual treatment received.

### 5.4. Protocol Deviations

Protocol deviations will be identified through a review of deviations captured by the Syneos Health site monitors and through programmatic checks on the database.

Protocol deviations include:

- Subjects not meeting eligibility criteria.
- Subjects who have been unblinded.
- Subjects taking prohibited concomitant medications during the study.

All protocol deviations will be listed, including a classification of major or minor. Major protocol deviations will be summarised overall and by deviation category for the Safety Population.

This document is confidential.

## 6. General Aspects for Statistical Analysis

### 6.1. General Methods

- Unless otherwise specified, summaries for Part A will be presented by cohort, dose level and overall, summaries for Part B will be presented by cohort, treatment, dose level and overall, and summaries for Part C will be presented by treatment and overall.
- Unless otherwise specified, continuous variables will be summarised using the number of observations (n), mean, standard deviation (SD), median, minimum, and maximum. Means and medians will be presented with one more decimal than the observed values. SD values will be presented with 2 more decimals than the observed values.
- Unless otherwise stated, categorical variables will be summarised using number of observations (n), frequency and percentages of subjects.
- Presentations for PK data are described separately in Section 9. Presentations for PD data are described in Section 10.
- All relevant subject data will be included in listings. All subjects entered into the database will be included in subject data listings.
- All statistical testing will be 2-sided with an alpha level of 0.05, with no adjustment for multiple comparisons.
- For Part B, formal statistical testing will focus on the 24 subjects treated at the doses used in Cohort 5 that were identified in Cohorts 3 and 4. These 24 subjects comprise the whole of Cohort 5, plus the 4 subjects from each of Cohorts 3 and 4 that were randomized with the selected dose/placebo.
- Where there are multiple assessments at a given time point, only the results recorded on the scheduled time point page of the case report form (CRF) will be used for summarisation, unscheduled assessments will be listed only.

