Part C will evaluate 111 subjects total (37 per treatment arm) aged ≥ 1 month to ≤ 36 months with an aim to have at least 34 evaluable subjects per treatment group. The primary endpoint will be the time-weighted average change from Baseline to Day 7 in RSV viral load measured in nasopharyngeal swabs by RT-qPCR comparing two dose levels of RV521 vs. placebo. Secondary endpoints will assess the safety, and efficacy of two dose levels of RV521 vs. placebo. Dose levels in Part C will be selected following the analysis of PK data, tolerability and safety from Part B. Two doses (RV521 age group specific high dose and RV521 age group specific low dose) will be selected for inclusion in Part C. The high dose will be selected for each age group to target approximately 90% of subjects achieving the target trough concentration for efficacy (3x EC₉₀), while not exceeding the upper safety limit, based on the paediatric PK model. The low dose will be selected such that the target trough level of 3xEC₉₀ is achieved in approximately 75% of the subjects. The high dose may be the highest tolerated dose from Part B, or a higher twice daily dose of RV521, depending on the safety, tolerability and PK data from Part B.

Subjects in Part C will be stratified by age (≥ 1 to < 6 months of age vs. ≥ 6 months to ≤ 36 months of age) and randomised in a 1:1:1 ratio. Both age strata will be enrolled in parallel. To maintain the double-blind, subjects randomised to placebo will be allocated to low volume (to match the volume associated with the lowest tested dose of RV521) or the higher volume (to match the highest tested dose of RV521).

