8.5.4 Method of Assigning Subjects to Treatment Groups

Part A:

Part A of the study is open-label and all subjects will receive RV521. The dose to be received by a given subject will be the dose currently being investigated, at the time the subject is enrolled, in the applicable cohort, as described in [Section 8](#).

Part B and Part C:

In Parts B and C, subjects will be randomised to treatment according to a central randomised list for each cohort. To protect the blind, the list will be produced by an unblinded biostatistician at Syneos Health who will be independent of the blinded statistician.

For Part B, subjects in Cohorts 3 and 4 will be randomised to RV521 or placebo (3:1). The randomisation list for Cohort 5 will be designed to ensure that the subjects who contribute to the final recruitment total of 24 are randomised to receive RV521 or placebo (2:1). The dose to be received by a given subject will be the dose currently being investigated at the time the subject is enrolled, in the applicable cohort, as described in [Section 8.1](#).

For Part C Cohort 6, the randomisation list will be designed such that the total of approximately 111 subjects (37 subjects per treatment group) will be randomised with an aim to have at least 34 evaluable subjects included in the analysis of viral load. Randomisation will be stratified by age

group (≥ 1 month to < 6 months vs. ≥ 6 months to ≤ 36 months) to ensure balance across the treatment groups, but there is no specified number of subjects that will be required in each stratum. Subjects will receive RV521 (age group specific low or high dose level) or placebo in a 1:1:1 ratio. Subjects randomised to placebo will be allocated randomly to either a low dose volume or a high dose volume to maintain the integrity of the double-blind design.

At the time of randomisation, a subject will be sequentially assigned to the next available treatment from the randomisation list for that cohort and stratum. Randomisation will be performed using an interactive web response system (IWRS). A blinded treatment kit (or > 1 kit, if required, in Part B and Part C), corresponding to the randomised treatment, will be allocated to each subject.

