### **Part C:**

Part C will be conducted in a single cohort (Cohort 6) in subjects  $\geq 1$  month to  $\leq 36$  months of age. Subjects will be randomised 1:1 to receive RV521 or placebo, according to the dose and regimen specified for their age group following completion of Part B (Cohort 5 subjects).

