#### **6.6. Subgroups**

For Study Part C, all tables for the primary efficacy endpoints of RSV-related signs and symptoms, RSV Clinical Scoring System score and supplemental oxygen use and all pharmacodynamics tables will be presented by the following subgroups:

- Duration of symptoms prior to randomisation: < 4 days or ≥ 4 days.
- Severity of illness at randomisation: RSV score < 9 (mild-moderate) or ≥ 9 (severe).
- Baseline RSV subtype by RT-qPCR (A or B or Both.)
- Presence or absence of other known respiratory pathogens at baseline.
- Age group (≥ 1 month to < 6 months or ≥ 6 months to ≤ 36 months at screening.)
- Other subgroups may also be presented.

This document is confidential.

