## **12.5. Vital Signs**

Vital signs include systolic blood pressure, diastolic blood pressure, heart rate, respiration rate, temperature and pulse oximetry. Temperatures captured in °F will be converted to °C using the conversion:

$$\text{Temperature (in } ^\circ\text{C)} = 5/9 (\text{Temperature [in } ^\circ\text{F]} - 32).$$

For each of Parts A, B and C, vital signs will be summarised at baseline and at each post-baseline time point. Summary statistics will be provided for the observed values at each time point, and the corresponding change from baseline. In addition, the investigator's interpretation of the vital signs are also captured. These data will be summarised at baseline and at each post-baseline time point.

Height, weight, body mass index (BMI) and head circumference will also be collected. The following conversions will be used:

$$\text{Height or circumference (in cm)} = \text{height or circumference (in inches)} * 2.54$$

$$\text{Weight (in kg)} = \text{weight (in lbs)} * 0.4536$$

$$\text{BMI (kg/m}^2\text{)} = \text{Weight(kg)}/[\text{Height(m)}^2]$$

Following conversion, the above vital signs will be presented to 1 decimal place.

This document is confidential.

For Parts B and C, height, weight, BMI and head circumference will be summarised at baseline and at each post-baseline time point. Summary statistics will be provided for the observed values at each time point, and the corresponding change from baseline.

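### Part C safety tables are not split by age group, although each active arm gives an age-group-specific dose and the protocol stratifies randomisation by age

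*SAP*

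**What the plan says.** **Layout of Part C tables.** SAP 6.1 gives the default for all summaries unless otherwise specified: "summaries for Part C will be presented by treatment and overall". For comparison, "summaries for Part B will be presented by cohort, treatment, dose level and overall".

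**Age split.** SAP 6.6 lists age group among the Part C subgroups. It limits them to the efficacy endpoints that the SAP calls primary and to pharmacodynamics: "supplemental oxygen use and all pharmacodynamics tables will be presented by the following subgroups". The only opening is "Other subgroups may also be presented", which is optional and stands in the same list.

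**Safety section.** SAP section 12 (adverse events, laboratory, vital signs, ECG, physical examination) sets no other layout for Part C. The table index in SAP section 19 names no Part C safety table by age or dose. For body size, SAP 12.5 says "For Parts B and C, height, weight, BMI and head circumference will be summarised at baseline and at each post-baseline time point", as observed values and change from baseline, without an age split.

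**Dose and randomisation.** Protocol section 3 states: "Two doses (RV521 age group specific high dose and RV521 age group specific low dose) will be selected for inclusion in Part C". SAP 3.9, although written for a one-dose Part C, also has RV521 given "according to the dose and regimen specified for their age group". Protocol 8.5.4 stratifies Part C randomisation by age group, "but there is no specified number of subjects that will be required in each stratum".

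**The concern.** In Part C, age group determines dose within an arm. The SAP accepts the same logic for Part B: section 15 drops dose from the models because, among the 24 subjects analysed, it duplicates age group. A Part C arm column can therefore average two doses, in proportions that depend on who happens to be enrolled.

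Protocol 7.2 makes safety against placebo a secondary objective of Part C. With the tables as planned, a reader who wants the adverse event rate at the dose given to infants under 6 months, or at the dose given to older children, will not find it in any summary. A harm limited to one stratum would be shown at reduced size.

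Age also matters for some safety variables in itself. The clinician ReSVinet scale (protocol 17.6) gives a normal respiratory rate of 40 to 50 under 2 months and 20 to 30 at 24 to 36 months. SAP 12.5 summarises respiratory rate in one column per arm.

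**Working it through.** **1. The plan's own figure.** The documents give no expected safety rates, so there is no safety figure to reproduce. The Part C sample size does reproduce. Protocol 11.2 assumes a difference of 1 log10, SD 1.25 and two-sided alpha 0.05; a two-sample t-test with 34 per group then has 90.2% power. Adding 10% gives 34 × 1.1 = 37.4, stated as 37. This point does not dispute that number; 37 per arm is used below.

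**2. Dilution formula.** Let *s* be the share of infants under 6 months, taken as the same in each arm because randomisation is stratified by age. Then

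pooled excess over placebo = *s* × (excess in young) + (1 − *s*) × (excess in older).

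If the excess in the older stratum is zero, the pooled excess is *s* × (excess in young). The strata may have different background rates; the formula still holds.

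**3. Illustration.** All rates and shares are assumptions: 30% in young infants at one active dose, and 5% in older children and on placebo. The excess in the young is 30 − 5 = 25 points.

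| Young share *s* | Young of 37 | Pooled rate in the arm | Pooled excess |
|---|---|---|---|
| 30% | 11 | 0.30 × 30 + 0.70 × 5 = 12.5% | 7.5 points |
| 40% | 15 | 0.40 × 30 + 0.60 × 5 = 15% | 10 points |
| 60% | 22 | 0.60 × 30 + 0.40 × 5 = 20% | 15 points |

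**4. Other assumptions.** Take a 10% background and 30% in the affected young infants, an excess of 20 points. With 7 of 37 young, the pooled table shows 20 × 7/37 = 3.8 points; with 18 of 37, 9.7 points; with 30 of 37, 16.2 points. The by-age table would show 20 points in each case, apart from sampling error.

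**5. What a by-age table can do.** Power of Fisher's exact test (two-sided 0.05), one active arm against placebo:

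| Assumed rates in the young | Young per arm | Within young stratum | Pooled, 37 per arm |
|---|---|---|---|
| 30% vs 5% | 11 | 13% | 8% |
| 30% vs 5% | 15 | 28% | 16% |
| 30% vs 5% | 22 | 51% | 36% |
| 30% vs 10% | 18 | 20% | 14% |

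Power is low either way. The gain is an undiluted estimate, not a reliable test.

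**6. Whether other planned output fills the gap.** Individual listings show events, not rates by arm. The DSMC review by age stratum (protocol 8.2) covers the first 9 subjects per stratum, 3 per arm, and takes place only if a dose higher than in Part B is selected. Neither gives final rates by arm and age.

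**The case against.** The case for leaving the tables pooled has several parts.

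- **Equivalent exposure.** Protocol 8.2 says that Part C doses will target the same exposure in both age groups. Each arm is then one exposure tier, and pooling has a rationale. This stands. But the target is model-based, and equal exposure does not establish equal tolerability; a by-age table would let that be checked.
- **The SAP predates the design.** SAP version 2.0 was issued before the Part A analysis. It describes a 1:1 Part C of about 120 subjects, stratified by symptom duration and severity (SAP 3.5 and 3.8.1). The missing layout is partly a product of that mismatch, and protocol 11.1 provides for Part C amendments before database lock and unblinding. This also stands, and it makes the amendment the natural place for the change.
- **Harm is watched during the trial.** The DSMC reviews Part C safety periodically and protocol 8.4.5 sets pausing criteria. These protect subjects but do not provide the final tables.
- **Small cells.** Splitting every table three arms by two strata gives sparse output of limited power. This is a fair reason to confine the split to the main tables.

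A reader might infer more than the documents support:

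- **That the arm comparison is biased by age.** It is not. Stratified allocation keeps the age mix similar across arms; only the overall mix is open.
- **That Part C alone pools ages.** Part B Cohort 5 spans 1 to 36 months, and its placebo subjects have no dose level to separate them by age.
- **That raw weight change hides poor growth to a known degree, so that age-standardised scores are required.** The documents give no growth figures and name no growth reference. Vomiting and diarrhoea would also be recorded as adverse events, and hydration status is summarised at each time point (SAP 8.6).

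**Conclusion.** The gap is real and easily closed. Where the two age-specific doses in an arm differ, no planned Part C safety table reports event rates at a dose actually given. Under the assumed rates, a 25-point excess confined to young infants would appear as 7.5 to 15 points at shares of 30% to 60%. The rates and shares are assumptions; the proportionality is not, provided that the harm is confined to one stratum and the age mix is similar across arms.

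The documents do not show that such a harm exists or is likely, and the equivalent-exposure target argues against assuming it. The point concerns what the tables can show, not a bias in the planned comparison. By-stratum tables would be descriptive. The change should be made in the Part C amendment to the SAP; it does not call the design or the sample size into question.

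**What to change.** When the SAP is amended for the current Part C design, before database lock and unblinding, extend the age-group split in SAP 6.6 to these Part C safety tables, and adjust SAP 6.1 to match:

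- the TEAE overview;
- TEAEs by system organ class and preferred term;
- treatment-related TEAEs and serious TEAEs;
- the vital-sign and weight-change summaries in SAP 12.5.

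Show each by arm within randomised age stratum, next to the pooled columns, and state that the by-stratum columns are descriptive.

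The cost is SAP wording and repeat runs of existing tables by a variable that SAP 6.6 already defines. Output becomes longer and some cells will be small: at a 30% young share, about 11 young infants and 26 older children per arm. Sample size, data collection and dosing do not change.
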